# CoMBAT OUD: Data Analysis Plan

**Protocol Title:** CoMBAT Opioid Use Disorder: A Pilot RCT of a Combined Medication and Behavioral Activation Treatment for People Living with Opioid Use Disorder.

**Principal Investigator (PI):** [name] [name], MPH; Behavioral and Social Sciences and Epidemiology, Brown School of Public Health; [contact]; [name]\[contact]

**Co-Investigators:** [name], MPH (UCLA); [name] (UMass Boston); [name], MPH (Boston University School of Public Health); and [name] (University of Denver)

---

This study is designed to explore the preliminary efficacy of the intervention on retention in Medications for Opioid Use Disorder (MOUD) care (primary outcome) and opioid use (secondary outcome) to inform a larger-scale R01 efficacy trial.

**Data Analysis.** The distribution of and correlations between all variables will be assessed. In the preliminary analyses, we will examine the randomization of groups with regard to baseline characteristics. In the unlikely event that randomization does not work to balance participant characteristics, we will run analyses with and without these variables to determine whether baseline differences account for differences in outcomes. If deemed appropriate, we will control for baseline characteristics. All analyses will use two-tailed tests of significance at  $p=0.05$ .

The primary quantitative analysis will compare engagement in care (number of missed doses & number of missed visits in the past 30 days) from baseline through the 6-month follow up visit by randomization arm. For the secondary outcome, we will examine changes in opioid use (as measured via urine toxicology screening) from baseline to the 6-month visit by randomized arm. While we expect some levels of care disengagement and opioid use across study conditions, we anticipate that those in the intervention arm will report fewer missed doses and visits and have fewer opioid-positive toxicology tests at follow-up than participants randomized to the control arm. For the primary outcomes, we will use generalized linear models (GLM) with properly-chosen link function (i.e., Poisson distribution) to analyze longitudinal data for each outcome. The GLMs will be estimated using generalized estimating equations (GEE) with robust standard error estimates. For the binary secondary outcome, we will use GEE models with a binomial distribution. We will follow an intent-to-treat model, analyzing participants according to their randomized study condition regardless of their intervention participation.

To assess feasibility and acceptability, we will conduct qualitative exit interviews with participants in both arms and administer the quantitative Working Alliance Inventory at the 3 month follow-up visit. The interviews will be transcribed, coded, and analyzed using thematic analysis. Participants' responses to the Working Alliance Inventory will be descriptively analyzed to assess perceptions of the therapist's empathy and engagement. We will also examine intervention attendance and study completion as an indicator of feasibility.

**Missing data.** We will assess patterns of missing data, which we expect to be low given our use of electronic data capture. If data are found to be missing, we will explore strategies for imputing missing data based on patterns of missingness and conduct sensitivity analysis to determine the optimal method of handling the missingness.

**Sample Size and Power.** This randomized controlled pilot trial is designed to assess feasibility and acceptability; thus, we are not powered to detect the preliminary efficacy of the primary and secondary quantitative outcomes. Nonetheless, in accordance with NIH policy, we will report our statistical findings on ClinicalTrials.gov.

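### Baseline adjustment depends on observed imbalance and later judgement, and the SAP leaves open how the baseline outcome enters the GEE; on one reading this costs precision

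*SAP*

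**What the plan says.** The SAP, under Data Analysis, first checks the randomised groups for balance. It continues: "In the unlikely event that randomization does not work to balance participant characteristics, we will run analyses with and without these variables", with the stated purpose "to determine whether baseline differences account for differences in outcomes". The next sentence is "If deemed appropriate, we will control for baseline characteristics". No characteristics are listed, no degree of imbalance is defined, and neither version is named as primary.

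The outcome models come in the following paragraph. "The primary quantitative analysis will compare engagement in care", measured as missed doses and missed visits over 30 days, "from baseline through the 6-month follow up visit by randomization arm". The binary urine endpoint is instead worded in terms of change: "we will examine changes in opioid use (as measured via urine toxicology screening) from baseline to the 6-month visit by randomized arm". On the model itself: "The GLMs will be estimated using generalized estimating equations (GEE) with robust standard error estimates". The link and distribution are indicated, but the terms in the model, the contrast and the working correlation are not.

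The protocol adds a separate commitment. Its Inclusion/Exclusion Criteria Justification says, without condition, that other services will be tracked and adjusted for. It does not say whether these are services at enrolment or later ones. The SAP does not mention them.

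**The concern.** Under randomisation, baseline imbalance is chance by construction. A covariate earns its place by predicting the outcome, and the size of an observed difference says little about that. For a repeated measure the obvious candidate is the baseline value of the same outcome, which the SAP's comparison from baseline already requires.

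The two paragraphs leave open whether that value is a covariate, a repeated response with its own mean in each arm, a repeated response with a common mean, or unused. These choices differ in precision, and the SAP says the pilot is meant to inform a larger efficacy trial. Adjusting for services that begin after randomisation is a further risk: they may be affected by arm, and conditioning on them could remove part of the effect.

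**Working it through.** **Inputs.** From the protocol: 16 per arm (minimum randomised) to 25 per arm (maximum); equal allocation by a random number generator with no stratification stated; baseline survey and urine test before randomisation; follow-up at 3 and 6 months. The documents give no outcome mean, variance, baseline-to-follow-up correlation or drop-out rate. These are assumptions below, shown as ranges. The plan states no figure of its own to reproduce.

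**1. How often the imbalance rule would be triggered.** For one characteristic in SD units, the difference between arms has standard error √(2/n).
- n = 16: √(2/16) = 0.354, so P(|difference| > 0.5) = 0.157.
- n = 25: √(2/25) = 0.283, so P = 0.077.
- At least one of five independent characteristics: 1 − (1 − P)⁵ = 0.575 and 0.330.
- At least one of ten: 0.819 and 0.552.
- With a p < 0.05 trigger instead: 1 − 0.95⁵ = 0.226 and 1 − 0.95¹⁰ = 0.401, at any sample size.

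The 0.5 threshold and the counts of five and ten are illustrative, since the SAP gives none.

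**2. Precision in closed form.** Take the 6-month contrast with equal variances, and let r be the correlation of the baseline and 6-month values. Relative to ignoring baseline, the variance is 1 − r² with a baseline covariate and 2(1 − r) for a comparison of changes with arm means free. The ratio of the second to the first is 2(1 − r)/(1 − r²) = 2/(1 + r).

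| r | covariate, 1 − r² | free arm means, 2(1 − r) | free / covariate |
|---|---|---|---|
| 0.1 | 0.99 | 1.80 | 1.82 |
| 0.3 | 0.91 | 1.40 | 1.54 |
| 0.5 | 0.75 | 1.00 | 1.33 |
| 0.7 | 0.51 | 0.60 | 1.18 |

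At r = 0.5, 25 per arm analysed with free arm means carries the information of 25 × 0.75 ≈ 19 per arm with baseline adjustment.

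**3. Check with Poisson GEE.** The simulated data were overdispersed counts capped at 30 with no treatment effect. The 24 main settings crossed 16 or 25 per arm; means of 0.5, 1 or 3 misses per 30 days; and log-scale correlations of 0.3 to 0.9 (count r 0.09 to 0.67), with 5,000 runs each. Variance ratios at 6 months:
- Free arm means against covariate: 1.14 to 1.77.
- Covariate against ignoring baseline: 0.58 to 1.04; with mean 0.5, only 0.93 to 1.04.
- Common baseline mean against ignoring baseline: 0.55 to 1.00 with an exchangeable working correlation; 1.00 (no gain) with independence.

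Twelve further settings had mean 1 and log-scale correlation 0.5 or 0.7. When 10% or 20% stopped MOUD and were scored as 30 missed doses, covariate against ignoring baseline was 1.02 to 1.04 and free against covariate 1.20 to 1.55. With 20% of follow-up visits missing at random, free against covariate was 1.33 to 1.93.

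**4. One setting in full.** Take 25 per arm, mean 1 and count r 0.22. The SD of the log rate ratio ignoring baseline is 0.434. The variance ratios are 0.95 (covariate) and 1.50 (free), giving SDs of 0.434 × √0.95 = 0.423 and 0.434 × √1.50 = 0.532. Around an estimated rate ratio of 1, the 95% intervals are about 0.44 to 2.29 and 0.35 to 2.83.

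**5. Effect of the trigger on the estimate.** When a p < 0.05 trigger fired in simulation, the adjusted and unadjusted 6-month rate ratios differed by a median factor of 1.11 to 1.28. One SD of sampling error (0.34 to 0.72 on the log scale) is a factor of 1.40 to 2.05.

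**The case against.** The strongest reply is that the SAP never adopts free baseline arm means. It gives no model terms, and its one directional expectation is fewer missed doses, missed visits and positive tests in the intervention arm at follow-up, which reads as a plain follow-up comparison. This stands. A reader might infer that the plan has committed to the less precise change contrast; the documents do not support that, so the 2/(1 + r) cost applies on one reading only.

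Against a follow-up comparison, the gain may be nil. Participants have been on MOUD for at least 30 days and those not planning to continue are excluded, so few baseline misses are plausible. Aim 1 counts care drop-out in the outcome, and scoring drop-out as 30 misses removed the gain in simulation. This also stands.

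A reader might infer that the discretionary rule inflates false positives. Reporting the smaller of the two p-values would do so (5.9% to 8.5% in a normal-outcome simulation with one covariate), but the SAP does not say it will. Its stated purpose for the paired analyses is a check, and adjusting only after a significant imbalance gave 3.4% to 4.5%. Nor does adjustment change what the primary rate ratio means: with a log link, randomised arms and no interaction, the adjusted and unadjusted ratios at a given visit have the same target. Only the odds ratio for urine results changes.

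Finally, the SAP says that "we are not powered to detect the preliminary efficacy of the primary and secondary quantitative outcomes". That limits the importance. It does not justify leaving the choice open when the data are few and the needed variable is already planned.

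**Conclusion.** The concern holds, at modest importance. The text supports three statements: adjustment is triggered by observed imbalance and then by discretion, without named covariates, a threshold or a designated primary version; the role of the baseline outcome in the GEE is unspecified; and the protocol's commitment on other services is absent from the SAP.

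The precision statement is conditional. Against a change contrast with free arm means, baseline adjustment was more precise in every setting examined, and the closed form gives the same direction for any r below 1. Against a follow-up comparison that ignores baseline, it ranges from a large gain (variance ratio 0.58) to a cost of about 4%. All sizes rest on assumed counts, correlations and drop-out. The trigger's own effect on the estimate is small beside sampling error.

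That later services would be adjusted for is possible, because the protocol gives no timing, but it is not stated. An unadjusted primary analysis is also a fair reading; the sentence on controlling for baseline where thought appropriate is what leaves it unsettled.

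**What to change.** Delete the imbalance-triggered rule and the discretionary sentence. For each outcome, name one primary GEE that includes the baseline value of that outcome as a covariate whatever the observed balance: for example log(count + 1) for missed doses and for missed visits, and the baseline urine result for the binary outcome. An acceptable alternative keeps baseline as a repeated response with a mean common to both arms and a stated working correlation other than independence. State the response visits and the contrast; that choice is the sponsor's.

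Label the unadjusted result a sensitivity analysis. For the binary outcome, say that the adjusted odds ratio is conditional on the baseline result, or report a standardised risk difference.

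Reconcile the protocol and SAP on other services: limit adjustment in the primary model to services recorded before randomisation, and report later ones descriptively.

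The cost is SAP wording, one degree of freedom per model, and up to about 4% in variance where misses are rare or drop-out dominates. The services point needs one defining sentence in the SAP or a protocol clarification. No new data are needed for the baseline covariates.

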Weekly Sessions. Regardless of intervention arm, participants are asked to take a brief weekly survey and provide urine for toxicology screening. Participants completing these study procedures remotely have the option of completing the survey online (via a REDCap link that is sent to them) or over the phone with a study team member. Participants who consent will then complete the weekly assessment over the phone or via a web-based link to the REDCap survey. Urine toxicology kits will be given to participants in-person or sent via mail. Participants will be asked to connect with a study team member via Zoom to show study staff the results of the urine test. Those in the intervention arm, will also be asked to complete their 50 minute counseling session with the therapist over the Zoom platform or by phone if they do not have access to the internet.

STUDY POPULATION AND SETTING

Number of Participants: We aim to enroll up to 50 individuals (25 per arm) who are currently receiving MOUD for opioid use in Massachusetts or Rhode Island and randomize a minimum of 32 participants (16 per arm).

Inclusion/Exclusion Criteria.

Inclusion Criteria	Exclusion Criteria

• Age 18 years or older• Initiated MOUD for opioid use \geq 30 day prior to screening• Current depressive symptoms• Plans to Rhode Island or Massachusetts for at least 6-months• Able to read, speak, and understand English• Willing and able to provide informed consent	
• Does not plan to continue taking MOUD• Unable to provide informed consent due to severe mental or physical illness, or substance intoxication at the time of interview• Discovery of active suicidal ideation at the time of interview• Pregnant and in second or third trimester• Enrolled or due to begin an intensive outpatient treatment program at the time of screening or enrollment

Inclusion/Exclusion Criteria Justification. The criteria were chosen to preserve methodological rigor and internal validity, while being attentive to the need for interventions that generalize to clinical populations.

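### With a logit link and an arm-by-visit contrast, an arm with no opioid-positive urines at 6 months makes the robust Wald p-value meaningless, mainly a risk at about 10-15% positivity or lower, and the SAP names no alternative

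*SAP*

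**What the plan says.** The SAP (Data Analysis) defines the secondary contrast as "changes in opioid use (as measured via urine toxicology screening) from baseline to the 6-month visit by randomized arm". On the model it says: "For the binary secondary outcome, we will use GEE models with a binomial distribution". The variance estimator is given just before, in the description of the primary-outcome models: "The GLMs will be estimated using generalized estimating equations (GEE) with robust standard error estimates". It is not restated for the binary outcome. All tests are two-sided at 0.05.

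The SAP does not state the link, the working correlation, whether visit is categorical or linear, a small-sample correction, or what happens if a cell is empty. The protocol (Study Population and Setting) aims for up to 25 per arm and a minimum of 16 per arm randomised. The SAP (Sample Size and Power) says the pilot is not powered for these outcomes, but adds: "we will report our statistical findings on ClinicalTrials.gov".

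**The concern.** With so few people per arm, one arm may have no opioid-positive test at 6 months. The maximum-likelihood log odds for that cell is then minus infinity (separation). Fitting stops at an arbitrary large negative value, and the sandwich variance does not register that the cell carries almost no information on the log-odds scale. The Wald test divides an arbitrary number by a small standard error.

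At stake is a chance split of one or two tests appearing as an overwhelming effect in a posted result and in the case for the larger trial. The SAP expects fewer positive tests under CoMBAT, and that hoped-for result is the one that makes an empty cell more likely.

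**Working it through.** **Inputs.** From the documents: 16 or 25 per arm, urine at baseline and 6 months, binomial GEE, two-sided 0.05. Assumed: logit link (canonical for the binomial), an arm-by-visit term, robust standard errors, and positivity from 5% to 20%. The documents give no positivity, retention or power figure, so there is nothing to reproduce first.

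**1. The contrast.** With cell proportions p, the arm-by-visit coefficient is

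b = [logit p(CoMBAT, 6 m) − logit p(CoMBAT, baseline)] − [logit p(TAU, 6 m) − logit p(TAU, baseline)].

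If p(CoMBAT, 6 m) = 0, b has no finite value.

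**2. Why the robust standard error stays small.** Under working independence, a person contributes (y − p)/(n·p(1 − p)) to the cell's logit. In an empty cell y = 0 for everyone, so each contribution tends to −1/n. The squared contributions sum to n × (1/n)² = 1/n, or 0.0625 at n = 16. The model-based variance, 1/(n·p(1 − p)), goes to infinity.

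**3. Worked example, 16 per arm.** Both arms have 3/16 positive at baseline; at 6 months TAU has 1/16 and CoMBAT 0/16. The TAU positive at 6 months is taken to be one of those positive at baseline. The value n·p(1 − p) is 2.4375 for 3/16 and 0.9375 for 1/16.
- TAU, contribution at 6 months minus baseline: one person 1 − 0.3333 = 0.6667; two people −0.0667 − 0.3333 = −0.4; thirteen people −0.0667 + 0.0769 = 0.0103. Sum of squares 0.4444 + 0.3200 + 0.0014 = 0.766.
- CoMBAT: three people −0.0625 − 0.3333 = −0.3958; thirteen people −0.0625 + 0.0769 = 0.0144. Sum of squares 0.470 + 0.003 = 0.473.
- Robust variance 0.766 + 0.473 = 1.239; SE = 1.113.

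The fit in statsmodels gives the same SE, stops at b = −21.86 and reports convergence: z = −21.86/1.113 = −19.6, p = 7×10⁻⁸⁶. Fisher's exact test on the 6-month counts gives p = 1.0, a fair benchmark because the baseline counts are equal. With an exchangeable working correlation the same data stop at −28.86, so the p-value depends on where the iterations end.

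**4. Bias-corrected sandwich.** Leverage is 1/n, so residuals are multiplied by 16/15. Variance 1.239 × (16/15)² = 1.409; SE = 1.187; z = −18.4; p = 1×10⁻⁷⁵. It does not help.

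**5. Other splits** (same baseline, working independence):

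| Positive at 6 months | b | Robust SE | Wald p | Fisher p |
|---|---|---|---|---|
| 1 vs 0 | −21.86 | 1.113 | 7×10⁻⁸⁶ | 1.00 |
| 2 vs 0 | −22.62 | 0.832 | 1×10⁻¹⁶² | 0.48 |
| 3 vs 0 | −23.10 | 0.688 | 2×10⁻²⁴⁷ | 0.23 |

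**6. Other specifications.** On these three splits, a common arm effect plus visit gives p of about 0.34 to 0.94. For 2 vs 0, model-based standard errors give p = 1.0. With a 3-month visit added, 2 vs 0 gives p = 0.35 under an identity link and 3×10⁻²³⁸ under a log link. Linear time over three visits stays finite, with p = 0.007 to 0.009.

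**7. How often.** P(no positives in an arm) = (1 − p)ⁿ, and P(at least one arm empty) = 1 − [1 − (1 − p)ⁿ]². For p = 10%, n = 16: 0.9¹⁶ = 0.185; 1 − 0.815² = 0.34.

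| Positivity, both arms | 16 per arm | 25 per arm |
|---|---|---|
| 5% | 69% | 48% |
| 10% | 34% | 14% |
| 15% | 14% | 3% |
| 20% | 6% | 1% |

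With TAU at 20% and CoMBAT at 10%: n = 16 gives 1 − (1 − 0.8¹⁶)(1 − 0.9¹⁶) = 1 − 0.972 × 0.815 = 21%. With 13 analysed per arm, 1 − 0.945 × 0.746 = 30%.

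**8. False positives.** A null simulation of the 6-month arm contrast (40,000 trials, full follow-up), counting fits with exactly one empty arm as significant, rejects in 50%, 30%, 14% and 6.5% of trials at 5%, 10%, 15% and 20% positivity with 16 per arm, and in 40%, 14%, 5.4% and 4.1% with 25.

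**The case against.** The strongest reply is that the SAP does not commit to the specification that fails. Link and visit coding are open, and robust standard errors are stated only for the primary models. A common arm effect, an identity link or model-based standard errors avoid the collapse. This stands against any claim that every binomial GEE with an empty cell fails. It does not remove the point. The logit is the canonical link, and a change from baseline to 6 months by arm is an arm-by-visit contrast; a common arm effect averages over baseline and does not estimate that change. If only those two visits are fitted, linear and categorical time are the same model.

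Second, a reader might infer that an empty cell is likely unless positivity is well above 20%. The arithmetic does not support this: at 20% in both arms it is 6% or 1%.

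Third, a reader might infer low positivity from the requirement of at least 30 days on MOUD. The documents also point the other way. The SAP expects some opioid use in both arms, no abstinence is required, depressive symptoms are an entry criterion, the protocol's background links depression to relapse, and the urine panel covers several opioids. No rate can be inferred in either direction.

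Fourth, this is a secondary outcome in a pilot declared unpowered, and an analyst who inspects distributions, as the SAP promises, may notice a coefficient near −22 beside a zero cell. That limits the consequence. But lack of power explains a null result, not a spurious extreme one, and the software gives no convergence warning.

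**Conclusion.** The point holds in a bounded form. Under the natural reading of the SAP (logit link, arm-by-visit contrast, robust standard errors), a 0% or 100% cell in one arm at 6 months gives a Wald p-value that carries no information, and the SAP provides no alternative.

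Its practical size depends on positivity and retention, for which the documents give no figure. With equal arms and full follow-up it is mainly a risk at about 10-15% positivity or lower: an empty cell in 34% (16 per arm) or 14% (25 per arm) of trials at 10%, and 14% or 3% at 15%. It also matters at a higher control rate if CoMBAT lowers use or participants drop out: 21% with 16 per arm, or 30% with 13 analysed, at 20% versus 10%. At 20% in both arms it is a minor risk.

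A reader might extend this to missed visits if one arm reports none. The documents give no basis for how often that would happen, so no size is claimed for it.

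**What to change.** In the SAP's Data Analysis section, for the urine outcome:

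- Keep the baseline-to-6-month arm contrast, and state the logit link and the arm-by-visit coding.
- Fit it with a Firth-type penalised logistic model so that the estimate stays finite, and take the p-value from a test that permutes the randomised arm between participants, in place of the robust Wald test.
- Name this as the governing test whatever the data show, so that the choice does not depend on finding an empty cell.
- Report the 6-month risk difference with a Miettinen-Nurminen score 95% confidence interval as the descriptive effect size.

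The cost is a few sentences in the SAP and a few lines of code. The test will be somewhat conservative at very low positivity.
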